7 INTRODUCTION

Obesity has reached global epidemic proportions as the prevalence has nearly doubled from 20 years ago. According to the World Health Organization (WHO), more than 1 billion adults worldwide are overweight, and at least 300 million are obese.¹ In the US, more than one-third of adults (35.7%) and almost 17% of children and adolescents are obese.² Obesity is a major risk factor for life threatening diseases such as type 2 diabetes mellitus (T2DM), heart attack, stroke, and some forms of cancer. For example, the age-adjusted relative risk of developing T2DM is approximately 10-fold higher for men with a body mass index (BMI) of 30 kg/m² relative to men with a BMI <23 kg/m² and the risk is even higher for women, where a BMI of 30 kg/m² is associated with an approximately 30-fold higher risk.^{3,4} Obesity is a major cause of morbidity and mortality, and it is estimated that there are 300,000 obesity-related deaths annually in the US alone.⁵

It is well established that modest weight reductions of 5% to 10% of body weight can decrease blood pressure (BP) and total blood cholesterol, improve glucose tolerance in diabetic patients and those with impaired glucose tolerance prone to develop diabetes, and reduce the severity of obstructive sleep apnea. Given the rise in the prevalence of obesity, even modest weight loss can be important to the overall health.

Current approaches to weight management include life style modification, pharmacotherapy and invasive bariatric procedures. Lifestyle modification involving a combination of diet, exercise, and behavioral change is the preferred and essential strategy for weight management in obese and overweight individuals. Although behavior modification can be very efficacious in some patients, adherence to the prescribed regimens is often poor. As such, lifestyle modification alone is often not adequate and the weight loss is often transient. On the other hand, bariatric surgery and various other invasive procedures are generally reserved for the severely obese population.

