8.3 EXPLORATORY OBJECTIVES

- To explore the effects of long-term treatment with lorcaserin HCl 10 mg BID on improving CV risk factors associated with obesity (eg, body weight, dyslipidemia, insulin level, hypertension, inflammatory biomarkers) compared with placebo at 1 year and yearly thereafter
- To evaluate the effect of BELVIQ (lorcaserin HCl) on other diabetes-related microvascular complications (retinopathy and neuropathy) compared to placebo in subjects with prediabetes or T2DM at Baseline at EOS. (revised per Amendment 01)
- To explore in subjects with a diagnosis of Non-Alcoholic Fatty Liver Disease (NAFLD) at Baseline, the effects of long-term treatment with lorcaserin HCl 10 mg BID on liver function compared with placebo at 1 year and yearly thereafter
- To evaluate echocardiographically determined heart valve and pulmonary artery pressure changes associated with treatment with lorcaserin HCl 10 mg BID compared to placebo at 2 years and yearly thereafter
- To collect and store DNA samples which may be used for examination of the impact of genetic variation on weight loss, the response to lorcaserin HCl, susceptibility to diabetes, and the risk of developing CV and other end-organ disease and their associated risk factors (for participating countries/sites where ethics and regulatory approval is obtained)
- To collect and store serum and plasma biomarker samples which may be used for examination of the impact of different metabolic and CV pathologic processes on weight loss, the response to lorcaserin HCl, susceptibility to diabetes, and the risk of developing CV and other end-organ disease and their associated risk factors (for participating countries/sites where ethics and regulatory approval is obtained)

- To explore the effects of long-term treatment with lorcaserin HCl (10 mg BID) on improvement of obesity-related complications, as defined by the 2014 Advanced Framework for a New Diagnosis of Obesity as a Chronic Disease (American Association of Clinical Endocrinologists [AACE] and American College of Endocrinology [ACE]) (eg, prediabetes, metabolic syndrome, hypertriglyceridemia/dyslipidemia, and potentially others) (revised per Amendment 01)
- To demonstrate that lorcaserin HCl 10 mg BID improves glycemic control, and/or reduction in OAD medications for the subjects treated with OADs compared to placebo at 6 months in the following subpopulations of patients with T2DM: (revised per Amendments 01 and 02)

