9.7.1.8 Exploratory Endpoints Analyses

- The change from Baseline in CV risk factors (body weight, BMI, waist and hip circumference, dyslipidemia, insulin level, hypertension, inflammatory biomarkers) will be analyzed using a mixed-effects model with repeated measures with treatment and stratification variable (presence of established CV disease or CV risk factors without established CV disease) as factors. Comparison between lorcaserin HCl and placebo will be made at 1 year. The ITT will be used for this analysis.
- For subjects with NAFLD at Baseline, the change from Baseline in liver function tests (AST, ALT, alkaline phosphatase, GGT, total and direct bilirubin) will be analyzed using

a mixed-effects model with repeated measures with treatment and stratification variable (presence of established CV disease or CV risk factors without established CV disease) as factors. Comparison between lorcaserin HCl and placebo will be made at 1 year. The ITT will be used for this analysis.

- The proportion of subjects who meet FDA-defined valvulopathy in echocardiographically determined heart valve changes will be analyzed using logistic regression including treatment as a factor and baseline BMI as a covariate. Comparison between lorcaserin HCl and placebo will be made at 2 years and yearly thereafter. The FDA-defined Valvulopathy Analysis Set will be used for this analysis.
- The change from baseline in eGFR and ACR will be analyzed using a mixed-effects model with repeated measures with treatment as a factor and baseline value as a covariate. Comparison of the trajectories for lorcaserin HCl and placebo will be made at 1 year, yearly thereafter, and at EOS. The ITT will be used for this analysis.
- The change from Baseline in echocardiographically-determined pulmonary arterial systolic pressure will be analyzed using a mixed-effects model with repeated measures with treatment as a factor and baseline BMI as a covariate. Comparison between lorcaserin HCl and placebo will be made at 2 years and yearly thereafter. The ITT will be used for this analysis.

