## 3.2.1 Exploratory Objectives

• To explore the effects of long-term treatment with lorcaserin HCl 10 mg BID on improving CV risk factors associated with obesity (eg, body weight, dyslipidemia, insulin

- level, hypertension, inflammatory biomarkers) compared with placebo at 1 year and yearly thereafter
- To evaluate the effect of BELVIQ (lorcaserin HCl) on other diabetes-related microvascular complications (retinopathy and neuropathy compared to placebo in subjects with prediabetes, or T2DM at Baseline at EOS. (revised per Amendment 01)
- To explore, in subjects with a diagnosis of Non-Alcoholic Fatty Liver Disease (NAFLD) at Baseline, the effects of long-term treatment with lorcaserin HCl 10 mg BID on liver function compared with placebo at 1 year and yearly thereafter
- To evaluate echocardiographically determined heart valve and pulmonary artery pressure changes associated with treatment with lorcaserin HCl 10 mg BID compared to placebo at 2 years and yearly thereafter
- To collect and store DNA samples which may be used for examination of the impact of genetic variation on weight loss, the response to lorcaserin HCl, susceptibility to diabetes, and the risk of developing CV and other end-organ disease and their associated risk factors (for participating countries/sites where ethics and regulatory approval is obtained)
- To collect and store serum and plasma biomarker samples which may be used for examination of the impact of different metabolic and CV pathologic processes on weight loss, the response to lorcaserin HCl, susceptibility to diabetes, and the risk of developing CV and other end-organ disease and their associated risk factors (for participating countries/sites where ethics and regulatory approval is obtained)
- To explore the effects of long-term treatment with lorcaserin HCl (10 mg BID) on improvement of obesity related complications, as defined by the 2014 Advanced Framework for a New Diagnosis of Obesity as a Chronic Disease (American Association of Clinical Endocrinologists [AACE] and American College of Endocrinology [ACE]) (eg, pre diabetes, metabolic syndrome, hypertriglyceridemia/dyslipidemia, and potentially others) (revised per Amendment 01)
- To demonstrate that lorcaserin HCl 10 mg BID improves glycemic control, and/or reduction in OAD medications for the subjects treated with OADs, compared to placebo at 6 months in the following subpopulations of patients with T2DM:

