## **5.1.4** Exploratory Endpoints

- Change from Baseline in CV risk factors at 1 year and yearly thereafter (e.g., body weight, dyslipidemia, insulin level, hypertension, and applicable biomarkers of CV risk and other end-organ diseases). For lipid parameters percent change from baseline will be used
- Change from Baseline in eGFR and ACR at 1 year, yearly thereafter, and at the end of the study. GFR will be estimated using creatinine, cystatin C and a combination of both (Section 8.1).
- Change from Baseline in LFTs (AST, ALT, alkaline phosphatase, GGT, total and direct bilirubin) at 1 year and yearly thereafter
- Proportion of subjects without FDA-defined valvulopathy at Baseline who develop FDA- defined valvulopathy at 2 years and yearly thereafter
- Change from Baseline in estimated pulmonary artery systolic pressure at 2 years and yearly thereafter
- Proportions of subjects with at least a 1-stage reduction in an obesity-related complication (prediabetes, metabolic syndrome, T2DM, hypertension, and hypertriglyceridemia/dyslipidemia) at 1 year and EOS; incidence of other obesity-related complications will be collected through AE reports, medical history, and use of

concomitant medications, based on 2014 Advanced Framework for a New Diagnosis of Obesity as a Chronic Disease (American Association of Clinical Endocrinologists [AACE] and American College of Endocrinology [ACE]). (revised per Amendment 01)

- Change from Baseline in HbA1c, FPG, fasting insulin levels, and homeostatic model assessment insulin resistance (HOMA-IR) at 6 months in the following subpopulations of subjects with T2DM at Baseline: (revised per Amendments 01 and 02)
  - o Subjects with (HbA1c>7%) at Baseline
  - o Subjects who have not been treated with antidiabetic agents at Baseline
  - o Subjects who are on monotherapy with oral antidiabetic agent at Baseline
  - Subjects with early T2DM (duration of diagnosis of diabetes is less than 5 years)
     at Baseline
- Proportion of subjects with reduction in the number of OAD medications or reduction in the dosage of OAD medications at 6 months in the following subpopulations of subjects with T2DM at Baseline: (revised per Amendment 01)
  - o Subjects with (HbA1c > 7%) at Baseline
  - o Subjects who are on monotherapy with oral antidiabetic agent at Baseline
  - Subjects with early T2DM (duration of diagnosis of diabetes is less than 5 years) at Baseline

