#### 5.8 EXPLORATORY ENDPOINT ANALYSES

• The change from Baseline in CV risk factors (body weight, BMI, waist and hip circumference, dyslipidemia, insulin level, hypertension, inflammatory biomarkers) will be analyzed using a mixed-effects model with repeated measures with treatment, month, month by treatment interaction and stratification variable (presence of established CV disease or CV risk factors without established CV disease) as factors and Baseline value as a covariate. Comparison between lorcaserin HCl and placebo will be made at 1year. The estimated treatment difference in the LSM between lorcaserin HCl and placebo, p-value, and the two-sided 95% CI will be calculated. The ITT will be used for this analysis. SAS PROC MIXED will be used using an unstructured covariance matrix (TYPE=UN). If the model fails to converge then other covariance structures such as; Heterogeneous Toeplitz covariance structure (TYPE= TOEPH), heterogeneous Autoregressive (TYPE=ARH(1)) or compound symmetry (TYP=CS) will be used.

- For subjects with NAFLD at Baseline, the change from Baseline in liver function tests (AST, ALT, alkaline phosphatase, GGT, total and direct bilirubin) will be analyzed using a mixed-effects model with repeated measures with treatment, month, month by treatment interaction and stratification variable (presence of established CV disease or CV risk factors without established CV disease) as factors and Baseline value as a covariate. Comparison between lorcaserin HCl and placebo will be made at 1 year. The estimated treatment difference in the LSM between lorcaserin HCl and placebo, p-value, and the two-sided 95% CI will be calculated. The ITT will be used for this analysis. SAS PROC MIXED will be used using an unstructured covariance matrix (TYPE=UN). If the model fails to converge then a Heterogeneous Toeplitz covariance structure (TYPE= TOEPH) will be used.
- The proportion of subjects who meet FDA-defined valvulopathy in echocardiographically determined heart valve changes will be analyzed using a logistic GLMM for repeated measures including treatment, month, month by treatment interaction as factors and baseline BMI as a covariate. Comparison between lorcaserin HCl and placebo will be made at 2 years and yearly thereafter. The odds ratio, p-value and 2-sided 95% CI will be calculated. The FDA-defined Valvulopathy Analysis Set will be used for this analysis.

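### CV risk-factor and liver-test objectives run to 1 year and yearly thereafter, but the arms are compared only at 1 year, so persistence would be described and not formally estimated

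*SAP*

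**What the plan says.** **Objectives.** Protocol 8.3 frames the first exploratory objective as one about duration: "To explore the effects of long-term treatment with lorcaserin HCl 10 mg BID on improving CV risk factors associated with obesity". Its timing is "inflammatory biomarkers) compared with placebo at 1 year and yearly thereafter". SAP 3.2.1 repeats this, and for subjects with NAFLD at Baseline it asks for "liver function compared with placebo at 1 year and yearly thereafter".

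**Endpoints.** SAP 5.1.4 lists "Change from Baseline in CV risk factors at 1 year and yearly thereafter" and gives the liver tests the same timing. The protocol synopsis and Protocol 9.7.1.1 match.

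**Analysis.** SAP 5.8 specifies a repeated-measures model for each endpoint family, with treatment, month, month-by-treatment, CV stratum and baseline value. It then fixes the contrast. For the risk factors, "Comparison between lorcaserin HCl and placebo will be made at 1year"; for the liver tests, likewise 1 year. Protocol 9.7.1.8 has, for both bullets, "Comparison between lorcaserin HCl and placebo will be made at 1 year. The ITT will be used for this analysis". The synopsis carries the same text.

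**Other reporting.** SAP 5.6.3 and 5.6.4 summarise laboratory values, blood pressure, weight, and waist and hip circumference by visit and treatment group. SAP 5.6 places these summaries on the Safety Analysis Set.

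**The concern.** An objective about long-term effect is paired with an analysis that stops at the first of its time points. The neighbouring bullets in SAP 5.8 do not stop there. eGFR and ACR are compared at 1 year, each later year and EOS, while valvulopathy and pulmonary artery pressure are compared from 2 years onward. So the restriction applies only to the risk factors and liver tests, and nothing in the text explains it.

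What is at stake is interpretation. Protocol 7.1 argues that a CV benefit could come through improved risk parameters. If MACE+ turns out neutral, readers will ask whether the between-arm difference in weight, lipids or blood pressure had narrowed by then. The visible plan has no prespecified estimate to answer with, and one produced after unblinding would be post hoc.

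**Working it through.** No stated figure needs reproducing. The check sets the texts side by side, then asks whether the later comparisons are feasible.

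**1. Timing at each level of the plan**

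| Level | CV risk factors | Liver tests |
|---|---|---|
| Objective (Protocol 8.3; SAP 3.2.1) | 1 year and later years | 1 year and later years |
| Endpoint (Protocol 9.7.1.1; SAP 5.1.4) | 1 year and later years | 1 year and later years |
| Comparison (Protocol synopsis, 9.7.1.8; SAP 5.8) | 1 year | 1 year |

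**2. Time points without a comparison.** Protocol Table 4 schedules these measures at Months 12, 24, 36 and 48, and SAP Table 8 defines yearly windows at the same months. That is 4 yearly points with 1 compared, so 4 − 1 = 3 have no specified contrast.

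**3. Was the omission recorded as a decision?** SAP Section 7 lists two exploratory analyses that were dropped. The later-year comparisons are not among them.

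**4. Can the SAP model supply them?** Yes. It contains month and month-by-treatment, so a treatment difference at each later month is a contrast from the same fit. Waist, hip, hsCRP and fibrinogen are scheduled only yearly after Baseline. For them a month-by-treatment term has content only if visits after Month 12 enter the model. The protocol's description of the model lists no month terms.

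**5. What is reported after year 1?** Descriptive summaries by visit and arm. They specify no between-arm difference, confidence interval or baseline adjustment. The liver-test summary is not restricted to NAFLD.

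**6. How many subjects could reach later years?** This rests on the planning assumptions in Protocol 9.7.2 and SAP Section 4 (54-month study, 15-month accrual), plus uniform accrual, before drop-out.
- Shortest potential follow-up: 54 − 15 = 39 months, so Months 24 and 36 are within reach of everyone retained.
- Month 48: enrolled in the first 54 − 48 = 6 of 15 months, 6/15 = 40%.

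These shares could be too high. Amendment 01, dated 06 Aug 2015, was still changing eligibility to allow recruitment, about 20 months after the December 2013 start. Someone enrolled after it would have at most about 38 months to October 2018. The stopping rule also requires only a median treatment duration of 2.5 years (2.5 × 12 = 30 months). If the trial stopped at that minimum, half the subjects would have 30 months of treatment or less.

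**7. Are the later data collected off drug?** In Table 4, chemistry carries footnote e: it stops after the EOT visit in subjects who discontinue drug early. Footnote f keeps only renal and glycemic parameters, so lipids and liver tests are not scheduled after that point. Weight, waist/hip and vital signs carry no such footnote.

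**The case against.** The strongest reply is that the later data are neither hidden nor lost. They appear by visit and arm in the safety tables, and later visits enter the repeated-measures model. This stands. A reader might infer that a waning effect would be passed off as the long-term effect, or that follow-up after year 1 goes unused. The documents support neither inference. What is missing is the prespecified adjusted difference and its interval.

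Second, SAP 5.5.2 and 5.5.3 promise separate pharmacodynamic and biomarker plans, and the protocol synopsis lists weight, blood pressure, lipids, insulin and the NAFLD liver tests under pharmacodynamic assessments. Yearly contrasts may sit there. This cannot be excluded, so the point concerns the visible plan. Even so, it would not explain why SAP 5.8 gives these endpoints a contrast at 1 year and omits the rest of their stated timing. SAP 5.7, which says no other analyses are planned, does not settle the matter either way.

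Third, the endpoints are exploratory and lie outside the MACE, MACE+ and T2DM-conversion hierarchy. This also stands and limits the weight of the point.

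Fourth, the protocol's remark that "lifestyle modification alone is often not adequate and the weight loss is often transient" concerns lifestyle change without drug. It makes durability a fair question, since both arms receive lifestyle instruction, but it is not evidence that the lorcaserin effect fades. Likewise, Protocol 7.1 speaks of improvement in risk parameters and does not say that the improvement must be sustained.

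**Conclusion.** The mismatch is real and present in both documents. For CV risk factors and for liver tests in NAFLD, three of the four yearly time points implied by the objective have no specified between-arm comparison. Persistence of the effect would be seen in descriptive tables but not formally estimated.

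The consequence is limited to an exploratory objective left partly unanswered. No primary or key secondary conclusion, event count or error rate changes.

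The conclusion needs no numerical assumption beyond the schedule. It is conditional on the separate pharmacodynamic and biomarker plans not already containing the contrasts, which the documents do not show either way. How informative Months 36 and 48 would be does depend on assumptions: full potential coverage at Month 36 and 40% at Month 48 hold only under 15-month uniform accrual and a 54-month study.

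**What to change.** In SAP 5.8, Protocol 9.7.1.8 and the protocol synopsis, extend the comparison in both bullets to 1 year and yearly thereafter. Report the least-squares mean difference with 95% CI at Months 12, 24, 36 and, where numbers allow, 48, all from the repeated-measures model already in SAP 5.8. Keep Month 12 as the lead time point. Show the number of subjects contributing in each arm at each month.

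The cost is a few extra contrast lines: no new data, no new model and no change to alpha. There is one real downside. Because lipid and liver-test chemistry is not scheduled after EOT in early discontinuers, the later contrasts for these variables would rest mainly on subjects still on drug, under a missing-at-random assumption. They should be labelled so. Weight, waist/hip and blood pressure are not subject to that footnote.

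If the sponsor intends 1 year only, the alternative is to narrow the objectives and endpoints to match and record the change in SAP Section 7. If the separate plans already hold the yearly contrasts, a cross-reference from SAP 5.8 is enough. Either way, the passages should agree before unblinding.

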- Change from Baseline in HbA1c at 6 months in subjects with T2DM at Baseline will be analyzed using an analysis of covariance (ANCOVA) model with treatment and stratification variable (presence of established CV disease or CV risk factors without established CV disease) as factors, and baseline HbA1c, as a covariate. Comparison between lorcaserin HCl and placebo will be made at 6 months. The estimated treatment difference between lorcaserin HCl and placebo and the 2-sided 95% CI will be calculated. The T2DM Analysis Set will be used for this analysis. (revised per Amendment 01)

In addition to the analysis of the ECHO data from this study, the following analyses will be repeated by pooling the ECHO data from this study with the data from the 3 pivotal lorcaserin

HCl studies (APD356-009, -010, and -011) with terms added for study and treatment by study interaction term in the model in order to account for the variability of the different studies.

- The proportion of subjects who meet FDA-defined valvulopathy in echocardiographically determined heart valve changes will be analyzed using logistic regression including treatment as a factor and baseline BMI as a covariate. Comparison between lorcaserin HCl and placebo will be made at 1 year. The FDA-defined Valvulopathy Analysis Set will be used for this analysis.
- The proportion of subjects with FDA-defined valvulopathy at Baseline who demonstrate worsened FDA-defined valvulopathy will be analyzed using logistic regression including treatment as a factor and baseline BMI as a covariate. A comparison between lorcaserin HCl and placebo will be made at 1 year. The ITT analysis set in subjects with FDA-defined valvulopathy at Baseline will be used for this analysis. (revised per Amendment 01)
- The change from Baseline in echocardiographically-determined pulmonary arterial systolic pressure will be analyzed using a mixed-effects model with repeated measures with treatment as a factor and baseline BMI as a covariate. Comparison between lorcaserin HCl and placebo will be made at 1 year and the corresponding 2-sided 95% CI will be calculated. (revised per Amendment 01) The ITT will be used for this analysis.

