- The change from baseline in eGFR and ACR will be analyzed using a mixed-effects model with repeated measures with treatment, month and month by treatment interaction as a factor and baseline value as a covariate. Comparison of the trajectories for lorcaserin HCl and placebo will be made at 1 year, yearly thereafter, and at EOS. The estimated treatment difference in the LSM between lorcaserin HCl and placebo, p-value, and the two-sided 95% CI will be calculated. The ITT will be used for this analysis. SAS PROC MIXED will be used using an unstructured covariance matrix (TYPE=UN). If the model fails to converge then a Heterogeneous Toeplitz covariance structure (TYPE=TOEPH) will be used.
- The change from Baseline in echocardiographically-determined pulmonary arterial systolic pressure will be analyzed using a mixed-effects model with repeated measures with treatment, month, month by treatment interaction as factors and baseline pulmonary arterial systolic pressure and baseline BMI as covariates. Comparison between lorcaserin HCl and placebo will be made at 2 years and yearly thereafter. The estimated treatment difference in the LSM between lorcaserin HCl and placebo, p-value, and the two-sided 95% CI will be calculated. The ITT will be used for this analysis. SAS PROC MIXED will be used using an unstructured covariance matrix (TYPE=UN). If the model fails to converge then a Heterogeneous Toeplitz covariance structure (TYPE= TOEPH) will be used.
- Change from Baseline in HbA1c, FPG, fasting insulin levels, and homeostatic model assessment insulin resistance (HOMA-IR), at 6 months in subjects with T2DM at Baseline will be analyzed using an ANCOVA model with treatment and stratification variable (presence of established CV disease or CV risk factors without established CV

disease) as factors, and baseline HbA1c, as a covariate. Comparison between lorcaserin HCl and placebo will be made at 6 months. The estimated treatment difference in the LSM between lorcaserin HCl and placebo, p-value, and the two-sided 95% CI will be calculated. The T2DM Analysis Set will be used for this analysis, in the following subpopulations.

- o Subjects with (HbA1c>7%) at Baseline
- o Subjects who have not been treated with antidiabetic agents at Baseline
- o Subjects who are on monotherapy with oral antidiabetic agent at Baseline
- Subjects with early T2DM (duration of diagnosis of diabetes is less than 5 years) at Baseline.

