- Proportion of subjects with reduction in the number of OAD medications or reduction in the dosage of OAD medications in the following subpopulations of subjects with T2DM at Baseline will be analyzed using logistic regression including treatment as factor. Comparison between lorcaserin HCl and placebo will be made at 6 months. The odds ratio, p-value and 2-sided 95% CI will be calculated. The T2DM Analysis Set will be used for this analysis, in the following subpopulations:
  - o Subjects with (HbA1c > 7%) at Baseline
  - o Subjects who are on monotherapy with oral antidiabetic agent at Baseline
  - Subjects with early T2DM (duration of diagnosis of diabetes is less than 5 years) at Baseline
- Proportions of subjects with at least a 1-stage reduction in an obesity-related complication (prediabetes, metabolic syndrome, T2DM, hypertension, and hypertriglyceridemia/dyslipidemia), incidence of other obesity-related complications will be collected through AE reports, medical history, and use of concomitant medications, will be analyzed using logistic regression including treatment as factor. Comparison between lorcaserin HCl and placebo will be made at 1 year and EOS. The odds ratio, p-value and 2-sided 95% CI will be calculated. The ITT Analysis Set will be used for this analysis.

Logistic regression including treatment as factor will be used for the following endpoints. Comparison between lorcaserin HCl and placebo will be made at EOS. The odds ratio, p-value and 2-sided 95% CI will be calculated.

The Prediabetes Analysis Set will be used for the following analyses: (revised per Amendment 01)

- Proportions of subjects with prediabetes at Baseline who develop new diagnosis of diabetic retinopathy at EOS.
- Proportions of subjects with prediabetes at Baseline who develop new diagnosis of diabetic neuropathy at EOS.

The T2DM Analysis Set will be used for the following analyses: (revised per Amendment 01)

- Proportions of subjects with T2DM at Baseline who develop new diagnosis of diabetic retinopathy at EOS.
- Proportions of subjects with T2DM at Baseline who develop new diagnosis of diabetic neuropathy at EOS.

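### SAP 5.8 adjusts 6-month change in FPG, fasting insulin and HOMA-IR for baseline HbA1c instead of each outcome's own baseline, which costs precision but causes no bias

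*SAP*

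**What the plan says.** SAP 5.8 describes a single ANCOVA for four outcomes, "Change from Baseline in HbA1c, FPG, fasting insulin levels, and homeostatic model assessment insulin resistance (HOMA-IR), at 6 months", in four subpopulations of the T2DM Analysis Set: HbA1c above 7%, no antidiabetic treatment, oral monotherapy, and diagnosis under 5 years ago. The model has treatment, the CV-disease stratum "and baseline HbA1c, as a covariate". The protocol says the same in the Synopsis (Exploratory Endpoint Analyses) and in 9.7.1.8.

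Protocol Table 4 schedules FPG and fasting insulin at Screening, Visit 2 and Month 6. The first model in SAP 5.8, for CV risk factors including insulin level, does adjust each change for its own baseline value.

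Three other features matter for the lesser changes:

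- eGFR and ACR change are modelled "with treatment, month and month by treatment interaction as a factor and baseline value as a covariate", with no stratum and no transformation of ACR.
- The 1-year valvulopathy models in SAP 5.4.3 are "logistic regression including treatment as a factor and baseline BMI as a covariate". For retinopathy and neuropathy, SAP 5.8 says "Logistic regression including treatment as factor will be used for the following endpoints" and names no other term.
- The CV risk factor and liver function models in SAP 5.8 do carry "month by treatment interaction and stratification variable". So do the secondary renal Cox models in SAP 5.4.3. SAP 5.4 drops the stratum on purpose from time-to-event models in populations without T2DM, where Table 1 shows only one stratum.

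**The concern.** An outcome's own baseline is usually the strongest single predictor of its change. Using HbA1c in its place leaves avoidable residual variance and leaves the result more exposed to chance baseline imbalance in the outcome itself. For insulin, the same SAP section uses own-baseline adjustment in one model and not in another, without a reason. A likely origin is Amendment 02, which added FPG, fasting insulin and HOMA-IR to the exploratory endpoints; the covariate appears to have stayed as it was for HbA1c alone.

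All these analyses are in subgroups, where precision is scarcer. In the HbA1c-above-7% subgroup the range of the only baseline covariate is also cut, which limits what it can explain. At stake is the width of the confidence intervals on the exploratory glycaemic results.

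**Working it through.** **Plan figure.** The documents state no SD, correlation, sample size or power for these endpoints, so there is nothing to reproduce. The correlations below are assumptions.

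**1. Variance ratio for the covariate.** Put baseline and 6-month values on unit SD. Let rho be the correlation of own baseline with the 6-month value, a that of baseline HbA1c with own baseline, and b that of baseline HbA1c with the 6-month value.

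- Residual variance of change, adjusted for own baseline: 1 − rho².
- Residual variance of change, adjusted for HbA1c: 2(1 − rho) − (b − a)².
- With b = a·rho (HbA1c predicts the later value only through own baseline), the ratio is VR = [2 − a²(1 − rho)] / (1 + rho).

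Examples:

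- rho 0.5, a 0.7 (FPG-like): (2 − 0.49 × 0.5)/1.5 = 1.17.
- rho 0.5, a 0.2 (insulin-like): (2 − 0.04 × 0.5)/1.5 = 1.32.

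| rho | a = 0 | a = 0.2 | a = 0.4 | a = 0.7 | a = 0.8 |
|---|---|---|---|---|---|
| 0.3 | 1.54 | 1.52 | 1.45 | 1.28 | 1.19 |
| 0.5 | 1.33 | 1.32 | 1.28 | 1.17 | 1.12 |
| 0.7 | 1.18 | 1.17 | 1.15 | 1.09 | 1.06 |
| 0.8 | 1.11 | 1.11 | 1.09 | 1.06 | 1.04 |

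The range is 1.04 to 1.54, or a standard error 2% to 24% larger (square roots 1.02 and 1.24).

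**2. Could the order reverse?** HbA1c adjustment wins only if 2(1 − rho) − (b − a)² < 1 − rho², that is, if |b − a| > 1 − rho. HbA1c would have to predict the change better than the outcome's own baseline does. With b = a·rho, |b − a| = a(1− rho), which never exceeds 1 − rho.

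**3. In power terms.** Power is Φ[(1.96 + 0.84)/√VR − 1.96]. An analysis with 80% power under own-baseline adjustment has about 74% at VR 1.17 and 68% at VR 1.33.

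**4. Bias check by simulation** (3,000 trials of 200 subjects, true effect −0.30, three correlation settings). Mean estimates were −0.298 to −0.302 under both adjustments. Simulated variance ratios were 1.19 (rho 0.5, a 0.7), 1.30 (0.5, 0.2) and 1.13 (0.7, 0.6), against 1.17, 1.32 and 1.11 from the formula. Adding HbA1c on top of own baseline left the variance essentially unchanged (ratios 0.998 to 1.006).

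**5. Stratum, linear models.** With an 80/20 split and a residual standardized gap d between strata, omitting the stratum gives VR = 1 + 0.8 × 0.2 × d². That is 1.0016 at d = 0.1, 1.006 at 0.2 and 1.04 at 0.5.

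**6. Stratum, logistic models.** Simulated with 3,000 subjects, treatment odds ratio 1.5 and stratum odds ratio 2 (all assumed). The standard error of the treatment log odds ratio without and with the stratum was 0.1946 and 0.1948 at 3% risk, and 0.1125 and 0.1128 at 10% risk. Mean z did not move (2.07 and 3.59 either way).

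**7. ACR scale.** For a lognormal outcome with log-SD s, raw-scale efficiency relative to the log scale is roughly s²/(exp(s²) − 1). At s = 1.0 this is 1/1.718 = 0.58; at s = 1.5 it is 2.25/8.488 = 0.27. Both SDs are assumed, and the formula ignores the baseline adjustment that the SAP plans, so these figures show direction and not the size of the gain.

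**The case against.** The analyses are exploratory, sit outside the gatekeeping procedure and carry no multiplicity control. Insulin is partly covered by the CV risk factor model, which uses its own baseline, though at 1 year and in the ITT set. SAP 9 and 11 place programming rules and table shells in separate documents, so the programs may already use the right covariate. No correlation comes from the documents. All of this stands and limits the consequence, but it does not make HbA1c the right covariate for the other three outcomes.

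Two stronger readings are tempting and do not hold:

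- A reader might infer that regression to the mean or baseline imbalance biases the treatment difference. Under randomization both arms regress alike; chance imbalance affects a given realisation and not the expectation.
- A reader might infer that the ECHO and renal models lose precision by omitting the stratum. The loss is about 0 to 4% of variance in the linear models and nil in the logistic ones. The secondary renal Cox models already include the stratum; only the exploratory eGFR/ACR model among the renal models with both strata lacks it. For the ECHO analyses pooled with the three earlier studies, the documents do not show that this stratum exists there.

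On ACR, the documents give category cut-offs but no distribution, so one cannot say that a few macroalbuminuric subjects dominate the mean. Relative change in ACR already enters the secondary renal endpoints through the 30% criteria.

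**Conclusion.** The covariate mismatch is real for three of the four outcomes and is worth correcting. Its cost is precision alone, and the 1.04 to 1.54 range depends wholly on the assumed correlations and on HbA1c acting through own baseline. The direction is safer than the size: it reverses only in the implausible case in step 2.

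The ACR scale is a lesser improvement of uncertain size. The stratum is a matter of matching the analysis to the stratified randomization, and no material gain should be claimed for it. The primary endpoints and the key secondary endpoint are untouched.

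**What to change.** 1. In SAP 5.8, replace baseline HbA1c in this ANCOVA with the baseline value of the respective parameter: FPG for FPG, insulin for insulin, HOMA-IR for HOMA-IR, HbA1c for HbA1c. Baseline HbA1c may stay as an additional covariate. This costs one wording change and uses data already scheduled.
2. Analyse ACR on the log scale and report geometric mean ratios. The cost is that results become ratios instead of absolute differences.
3. For consistency with the design, add the CV-disease stratum to the eGFR/ACR model, the study-only ECHO models and the T2DM-set retinopathy and neuropathy models, where both strata are present (30% and 20% of the trial in Table 1). Leave the pooled ECHO models and the prediabetes-set models as they are. The cost is one term in each model statement.
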